### f) **Questionnaires**

The following questionnaires will be completed by the subjects:

- a. Karolinska Sleepiness Scale (KSS). Values will be collected prior to their shift work (around 6pm) and during shift work (around 12 midnight and around 4 am). These data will be obtained prior to tDCS stimulation, after the third stimulation and after the 6th stimulation sessions. They will be asked to rate how sleepy they are according to the following scale:
  9. Extremely sleepy, fighting sleep
  8. Sleepy, some effort to keep alert
  7. Sleepy, but no difficulty remaining awake
  6. Some signs of sleepiness
  5. Neither alert nor sleepy
  4. Rather alert
  3. Alert
  2. Very alert
  1. Extremely alert
- b. Epworth Sleepiness Scale Score (ESS) at baseline and after the 6th stimulation session.
- c. Side Effects

**g) Actigraphy**

This device is the size of a small wristwatch that measures activity and is a non-invasive method of monitoring human rest/activity cycle. The instructions for the device use as well as a sleep diary will be provided. The data is then downloaded into a computer.

**h) Psychomotor Vigilance Test (PVT)**

The PVT is a sustained-attention, reaction-timed task that measures the speed with which subjects respond to a visual stimulus. The PVT is a simple task where the subject presses a button as soon as the light appears. The light will turn on randomly every few seconds. The purpose of the PVT is to measure sustained attention and give a numerical measure of sleepiness. The purpose of the PVT is to measure sustained attention, and give a numerical measure of sleepiness by counting the number of lapses in attention of the tested subject. Subjects will be provided with a min-IPAD and the PVT will be done prior to their shift work (around 6pm) and during shift work (around 12 midnight and around 4 am). Values will be obtained prior to tDCS stimulation, after the third stimulation and after the 6th stimulation sessions.

**i) Cognitive Performance**

In addition, subjects will also be asked to make judgements or decisions on stimuli such as words or images presented on a computer screen to track memory and thought process (cognitive performance).

#### j) Transcranial Direct Current Stimulation (tDCS)

The neuroConn DC stimulator (neuroCare Group, Munchen, Germany) will be used to provide the tDCS stimulation. This battery-powered device will be controlled with a microprocessor to ensure constant current at up to 2000  $\mu\text{A}$ . For safety, multistage monitoring of the output current and electrode/tissue impedance will be included. The device automatically shuts off if the impedance becomes greater than 50  $\text{k}\Omega$  to prevent electric shocks or burns. This device will be investigational only (not FDA approved). As above, tDCS is a non-significant risk (NSR) investigational device that meets the abbreviated Investigational Device Exemptions (IDE) requirements at 21 CFR 812.2(b) addressing labeling, IRB approval, informed consent, monitoring, records, reports, and prohibition against promotion for an NSR device study.

Figure 1. tDCS electrode array (anode only pictured). All five elements are standard silver-silver chloride EEG electrodes placed in a plastic cup which is then filled with a conductive gel.

We will use a custom set of silver/silver chloride electroencephalographic (EEG) electrodes (at location F3 according to the 10-20 system) as described in McKinley et al. These new electrodes were shown to be more stable over time, produce lower sensation levels, and produce fewer skin reactions when compared to standard sponge electrodes. Both the anode and cathode consist of a separate array of 5 EEG electrodes as pictured in Fig. 1. Each electrode has an inner diameter of 1.6 cm yielding a contact area of 2.01  $\text{cm}^2$  for each electrode. At 2 mA of supplied current, the average current density will be 0.199  $\text{mA}/\text{cm}^2$  as calculated by current (2 mA) divided by area (10.05  $\text{cm}^2$ ).

For the active anodal stimulation condition, tDCS will be applied at 2mA for 30 min. The anode will be applied to scalp location F3 according to the 10-20 EEG electrode placement system while the cathode will be placed over the contralateral (i.e. right) bicep. Electrodes will be secured using medical bandages, and connectivity will be ensured using highly conductive gel.

#### IV. Data Analysis

##### *Sample size:*

The sample size is selected such that we have power to detect differences in the mean reciprocal reaction time (mean 1/RT) and KSS, which are our co-primary endpoints. Differences from baseline in the co-primary endpoints will be assessed at Visit 6.

We plan to enroll a total of 45 subjects. We assume a screen failure rate and a loss to follow up rate of 40%. Thus, we anticipate at least 27 evaluable subjects. Once 27 evaluable subjects have completed the study, enrollment will stop. We will control the type I error rate at 0.10 for assessing the primary endpoints conservatively using a Bonferroni correction. With this sample size, we have 80% power to detect an improvement of 0.50 standard deviations in mean 1/RT with an alpha level of 0.05 using a one-sided t-test. For the KSS, we assume a standard

deviation of  $2^9$  and have 80% power with this sample size to detect a reduction in KSS of 1 with an alpha level of 0.05 using a one-sided t-test.

Statistical Methods:

The primary analysis will examine the difference in KSS and mean 1/RT at 4 AM at Visit 6 and baseline. To analyze differences in KSS at Visit 6 and baseline, and differences in mean 1/RT at Visit 6 and baseline, we will use paired t-tests using the worst values during the shift work. We will use Holm's Method to account for multiple testing and control the familywise error rate.

Secondary analyses will include the mean inverse response time and additional outcomes from the PVT and subjective questionnaires. To analyze differences in the number of lapses at Visit 4, we will use a Poisson regression model to compare the lapse rate at Visit 6 to the baseline rate. Additional questionnaires (ESS) will be assessed using paired t-tests.

We will also build longitudinal models to fully explore changes in outcomes both across weeks and within shifts. We may also explore joint models of subjective and objective outcomes to better characterize correlation between outcomes and their changes over time. Characteristics of participants will be summarized by randomized treatment group using appropriate descriptive statistics. We will also summarize any reported side effects of treatment. Additional exploratory analyses may be conducted at the discretion of the study team.

Interim Analysis:

An interim analysis will be conducted when 50% of the evaluable patients have reached the primary endpoint at Visit 6. That is, it will be conducted after 14 patients have an evaluable primary endpoint. The analysis will assess both co-primary endpoints using the error spending approach described by Lan and Demets. The study will be stopped early for efficacy if the p-value is less than 0.006 for both co-primary endpoints. If only one endpoint reaches the efficacy boundary, the trial will not be stopped early and will enroll the full planned number of participants.

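### The primary paired t-test uses only subjects who reach Visit 6 and sets aside Visit 3 data from those who leave later, so dropout related to response can bias the result in either direction

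*Combined protocol and SAP*

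**What the plan says.** Under Sample size, the time point is fixed: "Differences from baseline in the co-primary endpoints will be assessed at Visit 6". Under Statistical Methods, the test for KSS and mean 1/RT is stated: "we will use paired t-tests using the worst values during the shift work".

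Recruitment is described as follows: "We plan to enroll a total of 45 subjects"; "We assume a screen failure rate and a loss to follow up rate of 40" percent; "Thus, we anticipate at least 27 evaluable subjects"; and "Once 27 evaluable subjects have completed the study, enrollment will stop". The Interim Analysis section counts a subject as evaluable once the Visit 6 primary endpoint is available. No other definition of evaluable is given.

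An on-treatment measurement exists between baseline and Visit 6. For KSS, Detailed Procedures f) says: "These data will be obtained prior to tDCS stimulation, after the third stimulation and after the 6th stimulation sessions". Section h) gives the same schedule for the PVT. The only planned use of all three occasions is this: "We will also build longitudinal models to fully explore changes in outcomes both across weeks and within shifts". The plan names no analysis population, missing-data method or dropout sensitivity analysis. Subject compensation provides for prorated payment, so incomplete participation is foreseen.

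**The concern.** A paired t-test drops anyone without a Visit 6 value. Because recruitment runs to a count of completers, the 27 analysed are a selected subset of those treated whenever anyone leaves after starting stimulation. If leaving is related to benefit, the mean change in completers is not the mean change in treated subjects.

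The design offers nothing to offset this. There is no control arm in which similar selection would occur, and the completer mean is tested one-sided against zero. The interim efficacy look uses the same endpoint in the same kind of subject. The Objectives section says a positive result will be the basis of a confirmatory trial, so a false positive or a distorted effect size would carry forward.

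**Working it through.** **1. The plan's own figures.** Inputs from Sample size: n = 27, effect 0.50 SD (for KSS, 1 point with SD 2), one-sided alpha 0.05, 40% combined attrition.
- Paired t-test power = P(T > t(0.95; 26 df)), with T noncentral t and noncentrality 0.5 × √27 = 2.60. The result is 0.812, against the stated 80%.
- 27 / (1 - 0.40) = 45.

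Both reproduce. The sample size is not in dispute; the issue is bias and type I error.

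**2. Assumptions.** The 40% pools screen failures, who have no treatment data and cause no bias of this kind, with loss to follow-up. The documents do not split it and give no reason for loss. I therefore assume:
- a proportion of treated subjects is lost between Visit 3 and Visit 6;
- the log-odds of loss falls linearly with improvement at Visit 3 (slope per SD of change);
- Visit 3 and Visit 6 changes correlate 0.6;
- recruitment continues until 27 complete.

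**3. Formula.** If dropout depends only on the Visit 3 change, the bias of the completer mean (SD units) = 0.6 × (mean Visit 3 deviation among those who stay). At 20% loss and slope 1, those who stay average about 0.17 SD above the full group, and 0.6 × 0.17 = 0.10 SD.

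**4. Completer t-test with no true effect** (simulation, 6000 runs per setting for the 10-30% slope 1 and 2 settings):

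| Loss after Visit 3 | Slope per SD | Bias (SD) | Rejection at nominal 0.05 |
|---|---|---|---|
| any | 0 (unrelated) | 0 | 0.05 |
| 5-10% | 0.5-1 | +0.016 to +0.056 | 0.06-0.09 |
| 10% | 1 | +0.054 | 0.091 |
| 20% | 1 | about +0.10 | 0.125 |
| 20% | 2 | about +0.16 | 0.207 |
| 30% | 1 | not tabulated | 0.197 |
| 30% | 2 | +0.225 | 0.331 |
| 20% | 1, reversed | about -0.11 | below 0.05 |

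The moderate range (5-20% loss, slope 0.5-1) is about +0.02 to +0.10 SD with rejection of 6-13%. At the plan's KSS SD of 2, that is 2 × 0.02 = 0.04 to 2 × 0.10 = 0.20 points, against a 1-point target. With a true effect of 0.50 SD, 20% loss and slope 2, the completer estimate averages about 0.66 SD.

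**5. The alternative under the same mechanism.** A likelihood estimate that also uses the Visit 3 values of those who leave has bias of at most 0.007 SD and null rejection of 4.6-5.5%. Its standard error is about 0.19 SD, against 0.18-0.19 for the completer mean. Power at 0.50 SD is 79% (20% loss, slope 2) to 81% (10% loss, slope 1).

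**6. The alternative when its assumption fails.** If dropout depends on the unseen Visit 6 change, part of the bias remains:

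| Loss | Slope | Completer bias (SD) | Likelihood bias (SD) | Share removed |
|---|---|---|---|---|
| 10% | 1 | 0.092 | 0.061 | 0.031/0.092 = 34% |
| 20% | 1 | 0.174 | 0.116 | 0.058/0.174 = 33% |
| 20% | 2 | 0.263 | 0.185 | 0.078/0.263 = 30% |

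**The case against.** A reader might infer that the plan's estimate is bound to be too favourable. The documents do not support that. They state no dropout mechanism, and fitting three 60-minute visits a week around night shifts of at least 10 hours is a plausible reason for loss unrelated to response. The direction is therefore conditional, and this part of the objection stands in full.

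Loss may also be small. Treatment lasts two weeks, and half of the $500 compensation follows Visit 6, although payment is prorated. To yield 27 of 45, losses of 10%, 20% and 30% after Visit 3 imply screen failure of 1 - 0.6/0.9 = 33%, 1 - 0.6/0.8 = 25% and 1 - 0.6/0.7 = 14%. With the screening described, 14% looks low. The steepest setting is extreme: at 30% loss and slope 2, dropout is 65% at 1 SD below the mean Visit 3 change and 3% at 1 SD above. The 33% rejection rate is therefore an outer bound and not an expectation.

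The near-zero bias of the likelihood estimate in step 5 follows from the assumed mechanism, as step 6 shows. Subjects who leave before Visit 3 have no on-shift KSS or PVT after baseline, so the model learns nothing about their response on treatment.

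Finally, longitudinal models are already planned and the study is declared preliminary. But those models are only exploratory and have no stated missing-data role. In every setting examined, the Visit 3-based estimate had no more bias than the completer test and about the same standard error. The change is therefore more than a matter of taste.

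**Conclusion.** The structural point holds: a completer-only primary test, recruitment to a completer count, and Visit 3 data unused in that test. That leavers are replaced is an inference from the stopping rule, within the cap of 45; the plan does not use the word.

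The consequence is conditional: upward bias if poor responders leave, downward if good responders leave, none if dropout is unrelated to response. Under moderate assumptions the bias is about +0.02 to +0.10 SD with null rejection of about 6-13%. Steeper slopes or 30% loss give up to about +0.23 SD and 33%, and the reverse pattern at 20% loss gives about -0.11 SD. All of these rest on assumed loss rates, slopes and a correlation of 0.6. Neither certain inflation nor complete removal of bias by a repeated-measures model can be claimed. This is a cheap improvement that should be made, not a flaw that invalidates the design.

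**What to change.** In Statistical Methods, make the primary analysis of each co-primary endpoint a likelihood-based repeated-measures model with baseline, Visit 3 and Visit 6 and an unstructured covariance. Include all subjects who received at least one stimulation, and test the Visit 6 minus baseline contrast one-sided. Then:

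- keep stopping enrolment at 27 completers;
- keep the completer paired t-test as a sensitivity analysis;
- add a sensitivity analysis that assumes no change for subjects lost before Visit 3;
- report post-treatment loss with reasons, separately from screen failure.

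The cost is analysis-plan wording and a few lines of code, with no new visits, data or subjects. With complete data the contrast equals the paired mean difference, so little is lost if dropout proves negligible. The price is reliance on missing at random. That is a weaker requirement than the completer test's, which needs dropout to be unrelated to response. If dropout follows the unseen Visit 6 change, only about one third of the bias is removed.

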**V. Event Reporting**

(a) Adverse Events

The ICH Guideline for Good Clinical Practice E6(R1) defines an adverse event (AE) as:

Any untoward medical occurrence in a patient or clinical investigation subject administered a pharmaceutical product and which does not necessarily have a causal relationship with this treatment. An AE can therefore be any unfavorable and unintended sign (including an abnormal laboratory finding), symptom, or disease temporally associated with the use of a medicinal product, whether or not considered related to the medicinal product.

As this is a study that does not include a pharmaceutical product intervention, this definition would include AEs that occur as a result of protocol procedures and protocol treatment.

A serious adverse event (SAE) is any AE that:

- Results in death
- Is immediately life-threatening

This term refers to an event in which the subject was at risk of death at the time of the event; it does not refer to an event that may have led to death.

- Requires inpatient hospitalization or prolongation of existing hospitalization  
In general, hospitalization signifies that the subject has been detained (usually involving at least an overnight stay) at the hospital or emergency ward for observation and/or treatment that would not have been appropriate in an outpatient setting.
- Results in persistent or significant disability/incapacity  
The term disability means a substantial disruption of a person's ability to conduct normal life functions.
- Is an important medical event that may jeopardize the subject or may require medical intervention to prevent one of the outcomes listed above.

Medical or scientific judgment should be exercised in deciding whether expedited reporting is appropriate in this situation. Examples of medically important events are intensive treatment in an emergency room or at home for allergic bronchospasm, blood dyscrasias, or convulsions that do not result in hospitalizations; or development of drug dependency or drug abuse.

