#### 1. Collecting and reporting adverse events:

All AEs occurring after subject has signed consent and up to the study completion visit must be recorded on specific data collection forms.

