## 3. Data Safety Monitoring Plan

The risks involved with tDCS, completion of questionnaires, PVT, HSAT, and actigraphy are minimal.

This study will be monitored to ensure participant safety and data integrity. The monitoring for this study will be conducted by the Principal Investigator and the study team. The information that will be evaluated will be the incidence and severity of adverse reactions related to the study procedures, enrollment and efficiency of data capturing. The adverse events will be assessed on a case by case basis at the time the study team is aware of the event.

Overall study monitoring will take place on an ongoing basis with study review meetings taking place at least every 6 months. In the event the side effects suggest the risk outweighs the benefit, the study will be stopped and the IRB notified in order to evaluate possible solutions to the risk problem.

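### All adverse events are to be recorded, but the incidence reviewed in monitoring and the only planned safety summary cover only events regarded as related to study procedures or treatment

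*Combined protocol and SAP*

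**What the plan says.** Section V (a), Adverse Events, quotes a guideline definition under which an event counts "whether or not considered related to the medicinal product". Because the study has no pharmaceutical product, the section then says that "this definition would include AEs that occur as a result of protocol procedures and protocol treatment".

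Section V, Collecting and reporting adverse events, sets the recording rule: "All AEs occurring after subject has signed consent and up to the study completion visit must be recorded on specific data collection forms".

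The Data Safety Monitoring Plan names the principal investigator and study team as monitors and lists what they evaluate: "the incidence and severity of adverse reactions related to the study procedures, enrollment and efficiency of data capturing". It adds: "The adverse events will be assessed on a case by case basis at the time the study team is aware of the event".

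The Statistical Methods text in section IV has one sentence on safety: "We will also summarize any reported side effects of treatment". It plans no table of all AEs, and no section gives criteria for judging relatedness.

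**The concern.** The plan collects one set of events and commits to counting a smaller one. What separates the two is a judgement of relatedness. In a single-arm study in which everyone receives active stimulation, that judgement cannot be checked against a background rate, and the people named to monitor the study are those who run it.

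The disease under study makes this more than a formality. The Background section describes work accidents, falling asleep on shift and crashes on the morning commute as consequences of shift work disorder or night work. An event of that kind during the trial has a ready explanation other than the device.

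Two uses of the safety data are affected. The monitoring plan stops the study if side effects suggest that risk outweighs benefit, and the Objectives say that positive findings would lead to a larger confirmatory trial. Both are better served by a count that has not first passed through an attribution step. No efficacy result is affected.

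**Working it through.** The documents state no figure on this point, so the check is a comparison of texts.

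| Place | Function | Relatedness condition? |
|---|---|---|
| V (a), guideline definition | Defines an AE | None |
| V (a), adapting sentence | Carries the definition to a non-drug study | Unclear |
| V, Collecting and reporting adverse events | Recording | None |
| Data Safety Monitoring Plan, information evaluated | Incidence and severity in aggregate | Yes |
| Data Safety Monitoring Plan, case-by-case sentence | Individual assessment | None |
| IV, Statistical Methods | Reported safety summary | Yes, by its wording (effects of treatment) |
| V, Events Requiring Prompt Reporting | Prompt ethics-board report of serious events | Yes, as a reporting threshold |
| V, Additional Information | Summary at continuing review | Related events and other risk problems |
| V, Additional Information, last sentence | Prompt report of any event the investigator believes could affect safe conduct | None |

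**Tracing one event.** Suppose a treated subject crashes on the way home and the team attributes this to shift work disorder.

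1. Recorded: yes, on the plain reading of the recording rule.
2. Assessed individually: yes, under the case-by-case sentence. If it leads to hospitalisation it is also a serious AE, with no relatedness condition.
3. Counted in the incidence evaluated in monitoring: not required.
4. Included in the planned safety summary: not required.

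The gap lies at steps 3 and 4. Step 1 is exposed only if the adapting sentence is read as a causal restriction, because the recording rule takes its meaning of AE from that section.

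**Illustration of size.** The assumption is that one or two events are left out of the count; nothing in the documents supports a particular number. Take n = 27, the evaluable target in Sample size. The one-sided 95% exact upper limit p for x observed events solves P(X ≤ x | n, p) = 0.05.

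- x = 0: p = 1 − 0.05^(1/27) = 0.105
- x = 1: (1 − p)^27 + 27p(1 − p)^26 = 0.05 gives p = 0.164
- x = 2: adding the term 351p²(1 − p)^25 gives p = 0.215

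Reporting 0/27 where 1/27 occurred lowers the upper limit by 16.4 − 10.5 = 5.9 percentage points. Where 2/27 occurred, it lowers it by 21.5 − 10.5 = 11.0 points.

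**Denominator.** The figure of 27 is 45 × (1 − 0.40), where the 40% combines screen failure and loss to follow-up. The split is not given. If the trial runs to its 27 evaluable subjects, the number treated lies somewhere from 27 to 45. Subjects treated and then lost belong in a safety table, so 27 serves here only as a convenient n.

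**The case against.** A reader might infer that the protocol restricts the AE definition itself to events caused by study procedures. The text does not support this. The adapting sentence says that the definition includes such events and contains no limiting word. It follows a remark that there is no drug, so the natural reading is that drug-based wording is being extended to procedures and device. The serious-AE definition and the recording rule carry no relatedness condition. What stands against the sentence is that its causal phrasing sits awkwardly beside a definition that needs no causal link.

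A reader might also infer that events called unrelated escape safety evaluation altogether. They do not: individual assessment covers them, and the investigator may report promptly any event thought to bear on safe conduct. But individual assessment yields no incidence, the catch-all depends on the investigator's own belief, and neither adds anything to the planned summary.

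Third, the planned summary may involve no staff attribution at all. Side effects are listed among the questionnaires that subjects complete, and are scheduled at all six treatment visits. If that is the source, the input is participant-reported. This is fair, and the documents describe no staff filter before the summary. The summary is still of side effects and not of all AEs, and the questionnaire's content and recall period are not given.

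Fourth, the harm is hypothetical. The protocol excludes people with a past crash from falling asleep at the wheel, further exploratory analyses are allowed, and sleep-related events are common in night workers, so a fuller count would be hard to interpret without controls. All of this holds. It limits what the table can show, but it is not a reason to leave recorded events out of it.

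The related-only criterion for prompt ethics-board reporting is a reporting threshold and is not counted as evidence here.

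**Conclusion.** The concern holds in a limited form. The incidence evaluated in monitoring and the only planned safety summary are narrower than the AEs the protocol requires to be recorded. With no control arm, no stated relatedness criteria and no monitor named outside the study team, events attributed to shift work disorder need not appear in either, although they remain subject to individual assessment and to the safe-conduct catch-all. The definition section is ambiguous; it is not shown to be restrictive.

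This rests on reading the monitoring plan's list and the analysis sentence as they are written. The size is unknown. The shifts of about 6 and 11 percentage points show only what leaving out one or two events would do at n = 27, and they are not a forecast. The change is a cheap improvement to the safety reporting.

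**What to change.** 1. In the Data Safety Monitoring Plan, have all AEs recorded under section V reviewed in aggregate.
2. In Statistical Methods, plan a table of all recorded AEs for all treated subjects, not only the 27 evaluable, with investigator-assessed relatedness as a separate column and the basis for that judgement stated. The side-effects summary can stay beside it.
3. In section V (a), reword the adapting sentence so that an AE counts regardless of any relation to study procedures or treatment.

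The cost is protocol wording and one fuller table, since on the plain reading of the recording rule the data are already collected. The drawback is that the summary will hold more background events, which cannot be separated from device effects without a control arm. The relatedness column keeps the narrower view available.
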